8.2 Discussion of Study Design

An open-label design in which subjects are randomized to 1 of 2 treatment regimens (Cohort 2) or continue on 1 of these regimens (Cohort 1) from a previous clinical study (ND0612-006) was chosen for this Phase IIb safety study.

Following the recommendation of the ND0612-006 oversight committee the sponsor decided to discontinue Regimen 2 treatment on 08 December 2016. The decision was based on interim data from ND0612-006 that suggested that Regimen 2 (14 hr at a rate of 0.64 mL/hr) is suboptimal in respect to the therapeutic response as reflected by the daily "OFF" time, and therefore assessment of its long-term safety is not relevant. The sponsor decided to further evaluate an optimized daily treatment regimen of 16 hr at a rate of 0.75 mL/hr, and introduced treatment Regimen 3 in Protocol amendment 2.

Clinical studies have demonstrated that ND0612, at concentrations of up to 60 mg/mL LD and 14.0 mg/mL CD, can be administered for a continuous 24 hr period in healthy subjects and patients with PD and produce clinically relevant plasma concentrations of LD and CD with modest intersubject variability. This appears to be accomplished with minimal local dermal toxicity and with only mild and expected systemic toxicity. Total daily doses of ND0612 over 24 hrs have ranged to as high as 720 mg LD and 90 mg CD in study ND0612H-005, which was well-tolerated without significant AEs. This exposure is the same as the planned daily exposure of 720 mg LD/90 mg CD over 24 hrs in the current study for Regimen 1. Based on clinical experience so far, the local infusion site safety profile of ND0612 is favorable, local transient findings do generally not impact the subjects' general well-being and the drug's tolerability.

The variables used for assessing safety, tolerability, and efficacy are standard measures in clinical studies in PD subjects.

Subjects will be followed for at least 12 months to ensure that long-term safety and tolerability data can be collected. A special focus will be on local tolerability to ensure sufficient data for the evaluation of long-term local reactions at the infusion sites are being collected.

8.3 Selection of Study Population

8.3.1 Number of Planned Subjects

The aim is to include approximately 210 subjects who received study drug (ND0612) overall. This number of subjects should be sufficient for the evaluation of long-term safety and tolerability with a focus on local tolerability at the infusion sites. No formal sample size evaluation has been conducted. Rescreening is allowed in this study (see Section 9.1.1).

The study is planned to be conducted in about 65 study sites globally.

8.3.2 Inclusion Criteria

To be eligible for study entry subjects in **Cohort 1** (previously completed the treatment period in protocol ND0612H-006 within one month prior to enrolling to ND0612H-012) must satisfy all of the following criteria:

- 1. Subject is able to, and has signed an Institutional Review Board/Ethics Committee (IRB/EC)-approved informed consent form (ICF).
- 2. Subject has completed the treatment period of study ND0612H-006 not more than one month prior to enrolling in ND0612H-012.
- 3. Willing and able to administer the SC infusion alone or with the assistance of a study partner and able to comply with the study specific procedures.

To be eligible for study entry subjects in **Cohort 2** (ND0612 naïve subjects and subjects who completed treatment in a ND0612 clinical study more than one month before screening) must satisfy all of the following criteria:

- 1. Male and female PD subjects of any race aged at least 30 years who sign an IRB/EC-approved ICF.
- 2. PD diagnosis consistent with the UK Brain Bank Criteria.
- 3. Modified Hoehn & Yahr scale in "ON" state of stage ≤ 3 .
- 4. Taking at least 4 doses/day of LD/DDI (or at least 3 doses/day of Rytary) and taking, or have attempted to take, at least one other PD treatment for at least 30 days.
- 5. Subjects must be stable on their anti-PD medications for at least 30 days before Day 1.
- 6. Subjects may have had prior exposure to SC apomorphine injections/infusion but must have stopped continuous apomorphine administration at least 4 weeks before the screening visit. Treatment with apomorphine is prohibited during the entire ND0612 treatment period.
- 7. Must have a minimum of 2 hrs of "OFF" time per day with predictable early morning "OFF" periods as estimated by the subject.
- 8. Must have predictable and well defined early morning "OFF" periods with a good response to LD for treatment of the early morning "OFF" in the judgement of the investigator.
- 9. Mini Mental State Examination (MMSE) score ≥ 26 .

- 10. No clinically significant medical, psychiatric or laboratory abnormalities which the investigator judges would be unsafe or non-compliant in the study.
- 11. Female subjects must be surgically sterile (hysterectomy, bilateral oophorectomy, or tubal ligation), postmenopausal (defined as cessation of menses for at least 1 year), or willing to practice a highly effective method of contraception. All female participants must be non-lactating and non-pregnant and have a negative urine pregnancy test at Screening and at Baseline. Female subjects of childbearing potential must practice a highly effective method of contraception (e.g., oral contraceptives, intrauterine devices, partner with vasectomy), 1 month before enrollment, for the duration of the study, and 3 months after the last dose of study drug. Alternatively, true abstinence is acceptable when it is in line with the subject's preferred and usual lifestyle. If a subject is usually not sexually active but becomes active, the subject and sexual partner must comply with the contraceptive requirements detailed above.
- 12. Willing and able to administer the SC infusion alone or with the assistance of a study partner after a screening period of up to 40 days and willing and able to comply with study requirements.
- 13. Subjects should have a named study partner.

8.3.3 Exclusion Criteria

Subjects in **Cohort 1** and **Cohort 2** will be excluded from the study if one or more of the following criteria listed below are applicable.

1. Previously unable to tolerate ND0612 and/or have experienced intolerable adverse drug reactions associated with its use, regardless of the dosing regimen administered.

For **Cohort 2** the following exclusion criteria apply:

- 1. Atypical or secondary parkinsonism.
- 2. Acute psychosis or hallucinations in past 6 months.
- 3. Any relevant medical, surgical, or psychiatric condition, laboratory value, or concomitant medication which, in the opinion of the Investigator makes the subject unsuitable for study entry or potentially unable to complete all aspects of the study.
- 4. Any malignancy in the 5 years prior to randomization (excluding basal cell carcinoma of the skin or cervical carcinoma in situ that have been successfully treated).
- 5. Positive serum serology for Hepatitis B Virus (HBV), Hepatitis C Virus (HCV) or Human Immunodeficiency Virus (HIV) at the Screening visit.

- 6. Prior neurosurgical procedure for PD, or Duodopa treatment
- 7. Subjects with a history of drug abuse or alcoholism within the past 12 months.
- 8. Clinically significant ECG rhythm abnormalities.
- Renal or liver dysfunction that may alter drug metabolism including: serum creatinine >1.3 mg/dL, serum aspartate aminotransferase (AST) or alanine aminotransferase (ALT) >2 x upper limit of normal (ULN), total serum bilirubin >2.5 mg/dL.
- 10. Current participation in a clinical trial with an investigational product or past participation within the last 30 days before Day 1.

8.3.4 Removal of Subjects from Therapy or Assessments

A subject may withdraw or be withdrawn from the study for the following reasons:

- Subject withdraws consent, without the need to justify the decision
- Use of non-permitted concomitant therapy
- Non-compliance with the study drug or study schedule
- Lost to follow-up
- Pregnancy
- Occurrence of AEs not compatible with the continuation of subject participation in the study, in the investigator's opinion, or unacceptable to the subject to continue:
 - AE Infusion site reaction
 - $\circ \quad AE-Other$
- Investigator request to remove subject
- Lack of efficacy
- Sponsor request to remove subject or to terminate entire study
- Other; reasons have to be documented clearly in the source documents and electronic case report form (eCRF)

If the reason for early treatment discontinuation is "subject withdrew consent" or "other", the site will be asked to rule out the possibility of an AE. If an AE leads to study discontinuation, "AE – Infusion site reaction" or "AE – Other" should be chosen as the discontinuation reason instead of "subject withdrew consent" or "other".

Subjects who are withdrawn from the study and/or study treatment will not be replaced. Subjects are free to withdraw from the study at any time without prejudice to further treatment. The reason(s) for withdrawal will be documented in the eCRF.

Subjects withdrawing from the study will be encouraged to complete the same final evaluations as subjects completing the study according to this protocol, particularly

safety evaluations. The aim is to record data in the same way as for subjects who completed the study.

Reasonable efforts will be made to contact subjects who are lost to follow-up. These efforts will be documented in the subject's file.

The sponsor has the right to terminate the study at any time in case of serious AEs (SAEs) or if special circumstances concerning the study drug or the company itself occur, making further treatment of subjects impossible. In this event, the investigator(s) will be informed of the reason for study termination.

A DMC will meet periodically to review the accumulating safety data of the study and to provide a recommendation on study continuation or Early termination in case there is a concern regarding safety (see Section 10.3).

Pregnancy

Subjects will be instructed that known or suspected pregnancy occurring during the study should be confirmed and reported to the investigator, who will withdraw a pregnant subject from the study without delay and report the pregnancy within 24 hrs of first knowledge using a pregnancy report form. Upon discontinuation from the study, only those procedures that would not expose the subject to undue risk will be performed. The investigator should also be immediately notified of pregnancy occurring during the study but confirmed after completion of the study. In the event that a subject is found to be pregnant after inclusion in the study, any pregnancy will be followed to term, and after delivery, the status of mother and child will be reported to the sponsor after delivery.

Full details will be recorded on the withdrawal page of the eCRF.

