- Renal or liver dysfunction that may alter drug metabolism including: serum creatinine >1.3 mg/dL, serum aspartate aminotransferase (AST) or alanine aminotransferase (ALT) >2 x upper limit of normal (ULN), total serum bilirubin >2.5 mg/dL.
- 10. Current participation in a clinical trial with an investigational product or past participation within the last 30 days before Day 1.

Safety and Tolerability Assessment:

The primary endpoint in this study is a safety endpoint assessing the long-term safety (systemic and local) and tolerability of continuous SC infusion of ND0612 throughout the 12-month treatment period. Assessments, which constitute the primary endpoint of this study, will be based on AEs, with a focus on AESI, which will include infusion site reactions, hypersensitivity and polyneuropathy. Visual Analogue Scale (VAS) for pain assessment will also be used as primary measure. Tolerability will be assessed based on percentage of subjects completing 12 months of treatment in the trial, and the percentage of subjects who discontinued from the 12-month treatment period due to an AE.

Dopaminergic side effects including orthostatic blood pressure and changes in electrocardiogram (ECG) will be reviewed.

Safety and tolerability will furthermore be assessed based on laboratory parameters, vital signs, physical and neurological examination, assessment of suicidal behavior and ideation, assessment of excessive sleepiness, and assessment of impulsive compulsive behavior. The percentage of subjects that complete the 12-month study will be assessed.

For the subjects who continue to the optional treatment extension period only, and subjects who continue to the optional long-term treatment extension period, systemic and local safety of continuous SC infusion of ND0612 will also be assessed after up to 102 months of treatment based on AEs, with a focus on AESI, i.e., infusion site reactions, cases of hypersensitivity, polyneuropathy.

Efficacy Endpoints:

The exploratory efficacy endpoints assessed for 12 months of treatment are:

- Change in daily "ON" time without troublesome dyskinesia (defined as the sum of "ON" time without dyskinesia and "ON" time with non-troublesome dyskinesia) from Baseline to the 12-month visit based on home "ON/OFF" diaries.
- Change in daily "OFF" time from Baseline to the 12-month visit, based on home "ON/OFF" diaries
- Change in total daily dose of oral LD/DDI from Baseline to the 12-month visit.

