7 STUDY OBJECTIVES

7.1 Primary Objective

The primary objective of the study is to assess the long-term safety (systemic and local) and tolerability of continuous SC infusion of ND0612 for 12 months. Assessment will be based on adverse events (AEs), with a focus on adverse events of special interest (AESI), i.e., infusion site reactions, cases of hypersensitivity, polyneuropathy.

Tolerability will be assessed based on percentage of subjects that complete the 12-month treatment period of the study and the percentage of subjects who discontinue from the 12-month treatment period due to an AE.

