9.2.9 Unscheduled Visits

An Unscheduled visit may be performed at any time during the study at the subject's request or as deemed necessary by the investigator. Unscheduled visits will be scheduled e.g., if pump rate adjustments become necessary (see Section 8.4.9.2), when the subject has tolerability problems or has to down titrate the investigational treatment. Subjects should be advised that if tolerability problems continue then they should contact their investigator who may then withdraw them from the study. Subjects that complete the study and have unresolved nodules/skin problems at the last safety follow up visit will continue to be followed as considered necessary by the investigator.

At a minimum, concomitant medication data, AEs, and the date and reason for the Unscheduled visit will be recorded at this visit. Infusion site assessments will be performed and all infusion site reactions will be reported as AESI (see Section 10.1.3), whether or not considered clinically significant by the investigator.

When a subject attends an Unscheduled Visit between the scheduled visits they should be instructed to attend their next visit according to the study schedule as planned.

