11.1.3 Safety Variables

11.1.3.1 Primary Outcome Measures

The primary objective of the study is to assess the long-term safety (systemic and local) and tolerability of continuous SC infusion of ND0612 throughout the 12-month treatment period. Assessments, which constitute the primary endpoint of this study, will be based on AEs, with a focus on AEs of special interest (AESI) which will include infusion site reactions, hypersensitivity and polyneuropathy. VAS for pain assessment will also be used as primary measure. Tolerability will be assessed based on percentage of subjects completing 12 months of treatment in the trial, and the percentage of

subjects who discontinued from the 12-month treatment period due to a treatment emergent AE (TEAE).

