11.1.4 Primary Analyses

11.1.4.1 Methods of Analysis

Adverse events will be coded using the Medical Dictionary for Regulatory Activities (MedDRA). Adverse events will be grouped by system organ class (SOC) and preferred term (PT) and summarized by treatment regimen. Only treatment emergent AEs (TEAEs) will be summarized. TEAEs are defined as all AEs that start or worsen on or after the start of first study drug administration in the present study and before the start of the optional treatment extension (for the 1-year analysis). It is assumed that AEs that started in study ND0612H-006 will not be recorded on the case report form of the present study (unless the event in question worsened during the present study), as these

events will not be TEAEs in the present study. For subjects who do not participate in the optional treatment extension, events that start >28 days after the last dose of study medication will not be defined as TEAEs.

The summary tables will present the frequency and percentage of total subjects and number of events, by SOC and by PT.

For the summaries of AEs, subjects who experience the same AE (in terms of the MedDRA PT) more than once will only be counted once for that event in the number of subjects but all occurrences of the same event will be counted in the number of events. In addition, separate summaries will be provided for AEs by severity and relationship to study drug, as well as separate summaries for AEs leading to study drug discontinuation and SAEs.

In addition to the frequency counts and percentages, the AEs will be presented as annualized rates. The annualized rates will be calculated by the total number of reported AEs divided by the total exposure time, measured as the total subject years of exposure to the study medication.

The below listed summaries will be produced for the Safety Set. In general, all safety endpoints will be summarized using either summary statistics or frequency tabulations, as applicable to the type of data.

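### The percentage discontinuing due to an AE can be understated: the AE check covers only two withdrawal reasons, and the analysis counts TEAEs where the objective counts AEs

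*Protocol*

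**What the plan says.** **Withdrawal reasons.** Protocol 8.3.4 lists the reasons for withdrawal. The AE reason is broad: "Occurrence of AEs not compatible with the continuation of subject participation in the study, in the investigator's opinion, or unacceptable to the subject to continue", split into infusion site reaction and other AE. For two of the remaining reasons, withdrawn consent and other, "the site will be asked to rule out the possibility of an AE"; if an AE led to the discontinuation, one of the two AE codes replaces the reason. The list also contains "Non-compliance with the study drug or study schedule", non-permitted therapy, loss to follow-up, investigator request, lack of efficacy and sponsor request. No AE check is attached to these.

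**The measure.** Section 7.1 counts "the percentage of subjects who discontinue from the 12-month treatment period due to an AE", and the synopsis endpoint text agrees: "the percentage of subjects who discontinued from the 12-month treatment period due to an AE". Section 11.1.3.1 counts "subjects who discontinued from the 12-month treatment period due to a treatment emergent AE (TEAE"). Protocol 11.1.4.1.6, the statistical part of the synopsis, and SAP 2.1, 3.2.1 and 7.4.1 also say TEAE. A TEAE must start or worsen on or after the first dose in this study. For Cohort 1, section 11.1.4.1 adds: "It is assumed that AEs that started in study ND0612H-006 will not be recorded on the case report form of the present study". Only events that worsened are excepted.

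**Other places where an AE-driven stop appears.** Protocol 10.1.1 has AE action fields that include drug withdrawn and study drug stopped. SAP 7.3.4 plans a summary of TEAEs leading to treatment discontinuation. SAP 6.2 tabulates the reasons for premature discontinuation.

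**The concern.** The check in 8.3.4 exists because an AE can sit behind a neutral reason. The protocol describes further situations in which that can happen:

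- Section 9.2.9 tells subjects that "if tolerability problems continue then they should contact their investigator who may then withdraw them from the study". This could be entered as investigator request.
- Section 8.4.10 allows withdrawal of subjects who do not comply. Someone who stops wearing the pump because of site reactions could be entered that way.
- Section 8.4.9.1 requires withdrawal when a prohibited medication becomes necessary, even if an AE created the need.

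The change from AE to TEAE acts at a different point. A Cohort 1 subject may roll over directly from ND0612H-006. If that subject leaves because of an AE that began there and did not worsen, the disposition table can show an AE reason while the tolerability table shows nothing.

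The study is open-label and descriptive, with no formal testing, so the reported percentage is itself the result. Both gaps push it the same way, towards fewer AE discontinuations.

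**Working it through.** There is no planned rate, power or dropout figure to reproduce; protocol 11.2 and SAP 3.3 both say that no formal sample size evaluation was made. The check is a comparison of sections plus bounding arithmetic.

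**1. Which outputs are exposed**

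| Output | Depends on reason or AE coding? |
|---|---|
| Percentage completing 12 months | No |
| Kaplan-Meier time to discontinuation | No, all causes |
| Percentage discontinuing due to an AE/TEAE | Yes |

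**2. Which source feeds the exposed output.** Neither document says whether it is the disposition reason or the AE record. The answer decides which gap operates.

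- Disposition reason: a withdrawal entered under an unchecked reason is missed.
- AE record with TEAE flag: that same subject is counted if the AE was recorded with a withdrawal action, but a Cohort 1 carry-over AE is missed because it is assumed not to be on this eCRF.

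**3. Value of one missed subject**

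- Protocol planned size: 1/210 = 0.48 points.
- SAP planned size of 120-170: 1/120 = 0.83 and 1/170 = 0.59 points.
- Cohort 1, at most 36 subjects (protocol 11.2): 1/36 = 2.8 points.

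**4. Withdrawal-reason route.** Missed subjects = N × D × u × a, where D is all-cause discontinuation, u the share of withdrawals entered under an unchecked reason, and a the share of those that were AE-driven. All three are assumed.

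- Low: 210 × 0.20 × 0.10 × 0.10 = 0.4 subjects (0.2 points).
- Middle: 210 × 0.30 × 0.30 × 0.25 = 4.7 subjects (2.25 points).
- High: 210 × 0.40 × 0.50 × 0.50 = 21 subjects (10 points).

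**5. TEAE route.** Missed subjects = at most 36 × D × c, where c is the share of Cohort 1 discontinuations due to a non-worsened carry-over AE (assumed).

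- Low: 36 × 0.20 × 0.05 = 0.4 subjects (0.2 points of 210; 1 point of 36).
- High: 36 × 0.40 × 0.20 = 2.9 subjects (1.4 points of 210; 8 points of 36).

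For Cohort 2 the effect is near zero. The AE that stops treatment normally starts or worsens after the first dose. The exclusion of onset more than 28 days after the last dose removes nothing relevant, since such an AE cannot have caused the stop.

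**6. Scale.** The 95% half-width is 1.96 × √(p(1−p)/210). It is 4.1 points at p = 10% and 5.9 points at p = 25% (rates assumed).

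**The case against.** The best defence is that the plan already contains safeguards. The AE reason in 8.3.4 is wide enough to take a subject withdrawn for continuing tolerability problems, and 9.2.9 does not say that such a subject is entered as investigator request. Section 9.2.9 also requires AEs to be recorded at unscheduled visits and every infusion site reaction to be reported as an AESI. The AE action fields and the SAP summary of TEAEs leading to discontinuation can catch a subject whose disposition reason is wrong. This stands in part. These safeguards work only if the AE was recorded and marked as leading to withdrawal, and the summary also requires it to be treatment-emergent. No reconciliation with the disposition reason is planned.

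A second argument is that the two checked reasons are the ones that carry no cause, and that a site often cannot rule out an AE in someone it cannot reach. The point about loss to follow-up stands and limits the fix. It does not cover investigator request, which also states no cause, or non-compliance, which may have one behind it.

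Third, the Cohort 1 case should be uncommon. These subjects completed ND0612H-006 treatment, and those previously unable to tolerate ND0612 are excluded. Infusion sites change daily and a change in severity is a separate event, so a site reaction that prompts withdrawal will usually be new or worsened. This stands. The gap is narrow, but nothing in the plan closes it.

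A reader might infer that tolerability as a whole is made to look better than it is. The documents do not support that: percentage completing and the all-cause curve count every withdrawal whatever its code. Nor do they support any particular number of missed subjects.

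**Conclusion.** The percentage discontinuing due to an AE can be understated by two routes: an AE check limited to two withdrawal reasons, and a change from AE to TEAE between objective and analysis. The first can affect either cohort; the second is essentially confined to Cohort 1, at most 36 subjects (36/210 = 17.1% of the planned total). The source of the count is not named, so it is also unclear which route would apply.

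The direction and the value per subject (0.48 points of 210; 2.8 points of 36) are firm. The total is not: the ranges of 0.2 to 10 points and 0.2 to 1.4 points rest entirely on assumed discontinuation and miscoding shares, and the documents give no basis for choosing within them. The change is worth making because this is a primary tolerability measure, the error runs one way, and the remedy is cheap.

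**What to change.** 1. **Protocol 8.3.4.** Apply the AE check and the recoding rule to every withdrawal reason other than the two AE codes. For loss to follow-up, apply it as far as contact and existing AE records allow.
2. **Protocol 11.1.3.1 and 11.1.4.1.6, SAP 7.4.1.** Count a subject as discontinued due to an AE if either the disposition reason is one of the two AE codes, or any AE has the action drug withdrawn or study drug stopped, whatever its onset date. Using the disposition reason alone would rest the count on the field that may be miscoded. Reconcile the two sources before database lock, and show the TEAE-only count beside the main one. Align the synopsis and SAP 2.1 and 3.2.1.
3. **Cohort 1.** Record on this study's eCRF any AE that leads to discontinuation, even if it began in ND0612H-006, flagged as not treatment-emergent. Other AEs from that study need not be carried over.

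The cost is an eCRF edit check, a few more queries, a small addition to Cohort 1 data entry, and revised wording. The percentage may come out slightly less favourable. No clinical rule changes.
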